#### **10.4** Health Resource Use Other Than Hospitalizations

Information on health resource use including days unable to go to school/work, days unable to carry out usual activities, number of physician visits, number of clinical visits and number of emergency room visits are to be reported in electronic subject diaries.

Results are to be annualized by dividing the OPE in years of each subject with results obtained during the course of the study.

Information on other health resource usage is to be summarized for the FAS and listed for the SAS.

# 10.5 TGA Parameters, FVIII Trough Levels, Incremental Recovery and Comparisons against ABR

PK concentrations are to be obtained from the central laboratory and PK parameters based on the PK concentrations are to be derived by Baxalta. Further details on the calculation of PK parameters are to be documented separately.

PK concentrations and PK parameters for all analytes are to be summarized and listed for the PKAS.

Incremental recovery (IR) as derived below will be summarized for the SAF by visit including changes from baseline. IR will also be displayed graphically over time for each subject. All IR results will be reviewed by the medical team for plausibility. All IR results found not plausible by the medical team will be excluded from the analysis.

The following formula will be used to determine IR:

$$IR[(IU/dL)/(IU/kg)] = \frac{PostFVIII [IU/dL] - PreFVIII [IU/dL]}{Weight Adjusted Dose [IU/kg]}$$

where *PreFVIII* is the last available FVIII measurement prior to dose and *PostFVIII* the first FVIII measurement after dose.

FVIII trough levels and TGA results per subject are to be plotted in a scatter plot against the ABR of the three months after FVIII trough level and TGA measurement with a regression line overlaid on the individual points. The ABR of the three months after FVIII trough level and TGA measurement will be determined as described in Section 7.1: Bleeding Episodes and by counting the bleeds to the next scheduled visit (which is scheduled every three months).

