resulting in a clinical hypersensitivity reaction or increased clearance of BAX 855 from circulation. BAX 855 and ADVATE showed a similar immunogenicity profile in preclinical in vitro and in vivo studies. Data from preclinical studies indicate that PEGylated human FVIII can only induce antibodies against PEG when FVIII is recognized as a foreign protein that can provide immunogenic epitopes for CD4+ T cells. PTPs with a high degree of previous exposure to FVIII should be immunotolerant to FVIII and are considered to have a low risk of developing antibodies against FVIII. Therefore, the risk for PTPs with severe hemophilia A who do not have neutralizing antibodies against FVIII (inhibitors) of developing antibodies against PEG is considered to be rather low when treated with BAX 855. Moreover, results from a tissue cross reactivity study show that even high-affinity antibodies against PEG do not cross-react with any human tissue.

BAX 855 has been administered as a single dose of 30 IU/kg to 9 subjects and a single dose of 60 IU/kg to 10 subjects with severe hemophilia A in a Phase 1 study (Baxter clinical study 261101). Based on data from this study (see Section 6.4.2), there currently are no anticipated risks of BAX 855, beyond those associated with ADVATE, when administered in human subjects.

The comparability of BAX 855 to ADVATE, the preclinical safety profile of BAX 855, and the data from the Phase 1 study, suggest an acceptable risk benefit profile for BAX 855. Additional details related to risks and benefits can be found in the BAX 855 IB.

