Subjects receiving a PK-tailored prophylactic treatment regimen will have their PK assessment performed following eligibility confirmation. Following PK assessment, they undergo their baseline visit and subsequent visits every 3 months following their baseline visit for IR determination, efficacy and safety assessment and e-diary review. In addition, at 4, 8 and 18 weeks after the baseline visit, subjects' FVIII levels, TGA parameters and VWF antigen will be measured to ensure that FVIII trough levels of $\geq 3\%$ are maintained, and, if necessary, dose adjustments will have to be performed. Also, hemostatic efficacy and clinical safety will be assessed and e-diary reviewed.

Investigators will review e-diaries for untoward events, concomitant medications, non-drug therapies, and patient reported outcomes (PROs; see Section 10.5.2). Safety assessments performed at the study visit will include immunogenicity (inhibitory antibodies for FVIII and binding antibodies for FVIII, BAX 855, PEG, and CHO), and changes in conditions of the physical examination, vital signs, and clinical laboratory assessments (hematology, clinical chemistry, and lipids). Subjects who develop a high responder inhibitor (> 5 Bethesda Units [BU]), or who develop a low responder inhibitor (≤ 5 BU but ≥ 0.6 BU) that cannot be adequately managed by the prescribed prophylaxis regimen with BAX 855 will be discontinued from study. At every study visitⁱⁱⁱ, IR for FVIII activity and TGA parameters (optional in subjects receiving fixed dose prophylaxis) will be determined within 30 minutes prior to infusion with 60 ± 5 IU/kg BAX 855 and 30 ± 15 minutes following the infusion. Also, TGA parameters and pre-infusion VWF antigen level will be assessed in subjects receiving a PK-tailored dosing (optional for subjects aged < 12 years).

The sponsor will suspend enrollment and treatment if 2 or more subjects develop anaphylaxis after BAX 855 treatment. The sponsor may stop this study at any time. In addition, the sponsor may modify the study based on results of the other BAX 855 studies.

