13.4.3 Pharmacokinetics

For subjects undergoing a PK assessment in this study, the following PK parameters for FVIII will be reported using descriptive statistics: $AUC_{0-\infty}$, $T_{1/2}$, MRT, CL, IR, C_{max} and V_{ss} .

For subjects undergoing a PK assessment in this study, an exploratory analysis of correlation of baseline VWF antigen to BAX 855 PK will be performed as well as the possible influence of any anti-PEG antibodies (preexisting or detected during study participation) on the PK of BAX 855, if applicable.

IR will be summarized by visit and displayed graphically over time for each subject. Also the change from the baseline will be described using summary statistics.

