#### 5.4 Handling of Missing, Unused, and Spurious Data

Except for the below specified, missing data is not to be imputed.

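### SAP 10.5 does not tie the two FVIII values behind incremental recovery to one infusion, and then removes results on unwritten plausibility grounds

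*SAP*

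**What the plan says.** SAP 10.5 gives IR as post-dose FVIII minus pre-dose FVIII, divided by the weight-adjusted dose. PreFVIII "is the last available FVIII measurement prior to dose and" PostFVIII "the first FVIII measurement after dose". It states no time window, no same-infusion condition and no choice between the one-stage and chromogenic activity assays that Protocol 12.7.4 provides for.

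It continues: "All IR results will be reviewed by the medical team for plausibility". Then: "All IR results found not plausible by the medical team will be excluded from the analysis". It does not say what counts as implausible, when the review takes place, whether the reviewers have seen antibody results, or whether exclusions are listed.

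The protocol is tighter on sampling. Under Protocol 8.2, FVIII activity for IR "will be determined within 30 minutes prior to infusion", with a second sample 30 ± 15 minutes after it. The laboratory schedule in 20.4.1 agrees, but Protocol 12.7.4.3 has 30 ± 5 minutes. Protocol 13.4.3 plans the analysis without any plausibility exclusion: "IR will be summarized by visit and displayed graphically over time for each subject", together with change from baseline. SAP 5.7, which lists departures from the protocol's analysis, does not mention the exclusion.

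On missing data, SAP 5.4 says: "Except for the below specified, missing data is not to be imputed". Its list includes a carry-forward for body weight and nothing for FVIII.

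**The concern.** There are two linked gaps. First, if a sample is missing, the wording of SAP 10.5 still supplies a number. It reaches back to an earlier visit for the pre-dose value, or forward to a later visit for the post-dose value. That is a carry-forward (or carry-back) which SAP 5.4 does not declare, and in some visit patterns the result has nothing to do with recovery.

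Second, the only safeguard is a judgement on the IR value itself, in an open-label study, with no written rule. An artefact near zero and a genuine low recovery look alike on that scale, so the same act can remove either. The per-protocol set in SAP 4.4 shows a better practice: candidate reasons are listed and approval is required before database lock. IR review has neither.

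At stake are the IR summaries by visit, the changes from baseline and the per-subject graphs. These are descriptive, but they are the planned picture of recovery over time.

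**Working it through.** **The protocol's own figure.** Protocol 8.7.3.5 gives an anticipated recovery of 2.5 (IU/dL)/(IU/kg) and a reciprocal of 0.4. Check: 1/2.5 = 0.4. It reproduces. The SAP states no expected IR, standard deviation, missing rate or plausibility limit.

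**Inputs.** IR dose 60 ± 5 IU/kg and washout 84 to 96 h (Protocol 12.7.4.3); median half-life 13.60 and 16.64 h (Protocol 6.4.2); recovery 2.5. Assumptions: single-exponential decay, and a last prophylactic dose of 45 IU/kg, with 80 IU/kg as a range check.

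**One case in full** (half-life 13.60 h, washout 84 h):
- pre = 45 × 2.5 × 2^(−84/13.60) = 1.56 IU/dL
- post at 30 min = 1.56 + 60 × 2.5 × 2^(−0.5/13.60) = 147.8 IU/dL
- IR = (147.8 − 1.56)/60 = 2.44

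**The SAP rule read literally, over the full input range:**

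| Situation | Value picked up | IR |
|---|---|---|
| Complete pair | pre 0.84–3.40, post 147.1–150.3 | 2.44–2.45 |
| Post missing, routine IR visit | a later trough after washout | 0.00–0.04 |
| Pre missing, fixed-dose follow-up visit | previous visit's post-infusion peak | 0.00 if both doses are 60 |
| Pre missing, PK-tailored visit preceded by a trough | trough of 3–10 IU/dL (assumed) | 2.28–2.46 |
| Pre missing, ED1 in naïve subjects | screening value after washout | nearly correct |
| 15-min sample missing at the PK visit, age ≥ 12 | 3 h sample | 2.14–2.20 |
| 15-min sample missing at the PK visit, age < 12 | 9 h sample | 1.57–1.71 |
| Post missing, end of study | none | missing |

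Row 2, upper end: (80 − 45) × 2.5 × 2^(−84/16.64)/60 = 0.04. Row 3 with unequal doses inside 60 ± 5: (55 − 65) × 2.5/55 = −0.45 and (65 − 55) × 2.5/65 = +0.38. Row 5: each 1 IU/dL of difference in the pre value moves IR by only 1/60 = 0.017. The PK-visit rows apply only if this formula is used for the PK infusion.

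Most dose and level pairs in Protocol Table 3 imply a recovery of 2.0. With that value a complete pair gives 1.95–1.96 and row 3 runs from −0.36 to +0.31, so the pattern is the same.

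**If artefacts are kept.** With a share m of pairs at zero, the mean is 2.5 × (1 − m): 2.475, 2.45, 2.375 and 2.25 for m = 1%, 2%, 5% and 10%. These shares are assumed.

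**If genuine low values are removed.** Suppose 5% of results truly average 0.5. The mean of all values is 0.95 × 2.5 + 0.05 × 0.5 = 2.40. In a simulation with an assumed lognormal CV of 20–30%, a cut-off at 1.0 removes 99–100% of the true lows and the mean becomes 2.50. If the low 5% average 1.0, the full mean is 0.95 × 2.5 + 0.05 × 1.0 = 2.425, and cut-offs of 1.0 to 1.5 remove about 54–98% of them. The low-recovery rates and cut-offs are assumptions, not figures from the documents.

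**Sampling window.** For a recovery of 2.5, sampling at 15 or 45 minutes instead of 30 gives 2.47 or 2.41 against 2.44 (half-life 13.60 h), a shift of about 1.3%. The ± 5 and ± 15 minute texts need reconciling, but the numerical effect is small.

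**The case against.** The best reply is that SAP 10.5 should not be read alone. SAP 5.4 bars imputation and lists no exception for FVIII, SAP 5.6 presents data by nominal visit, IR is summarised by visit, and the protocol takes both samples around one infusion. Read together, the two values are those of that visit. This reading is reasonable and may be what was intended. It does not settle the matter, because the formula's wording points the other way and a programmer will code the formula.

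A reader might infer that every missing sample turns into an IR near 0. The documents do not support that. The pre-sample at ED1, PK-tailored visits preceded by a trough, the PK visit and the end-of-study post-sample all behave differently, as shown above.

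A reader might also infer that the exclusion hides the immunogenicity signal. That goes too far. Inhibitors and binding antibodies are measured directly (Protocol 12.7.6), and the inhibitor analysis in SAP 8.3 uses central-laboratory results that the IR review does not touch. Protocol 6.5 describes anti-PEG antibodies as possibly "resulting in a clinical hypersensitivity reaction or increased clearance of BAX 855 from circulation". That concerns clearance, not recovery half an hour after infusion.

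Three further points have weight. The review would probably catch most near-zero artefacts, so the two faults partly offset each other. The SAP does not equate low with implausible. Laboratory results are listed in full under SAP 8.2, so a determined reader could probably recompute IR. None of these supplies a rule for telling an artefact from a real value, and none shows which values were dropped.

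**Conclusion.** The point holds in limited form. SAP 10.5 contains two stated rules that can give wrong IR results. Followed literally, a missing post-sample at a routine IR visit, or a missing pre-sample at a fixed-dose follow-up visit, yields about 0 instead of about 2.5. Removal by judgement on the value can then take out genuine low recoveries along with artefacts, with no record of which was which.

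The size of any bias in the by-visit and change-from-baseline summaries cannot be stated, since the documents give neither a missing-sample rate nor a low-recovery rate. The illustrations rest on single-exponential decay, the Phase 1 half-lives, a recovery of 2.0 to 2.5 and assumed shares.

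The consequence is modest. IR is descriptive, is not among the outcome measures in Protocol 8.4, and does not feed the primary inhibitor endpoint. The change is still worth making because it is cheap and removes an avoidable source of bias.

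**What to change.** In SAP 10.5:

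- Compute IR only from the pre-infusion sample taken within 30 minutes before the dose and the scheduled post-infusion sample of the same infusion. Otherwise set IR to missing, in line with SAP 5.4.
- Reconcile the post-infusion windows in Protocol 12.7.4.3 (30 ± 5 minutes) and Protocol 8.2 and 20.4.1 (30 ± 15 minutes), and refer to the agreed one.
- Name the FVIII activity assay used in the formula.
- Exclude a value only for a documented dosing, sampling or assay error, decided without sight of antibody results.
- List each exclusion with its reason, and summarise IR with and without exclusions.

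The cost is a few lines of SAP text, one extra table and slightly more missing IR values.

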8.7.3.3 PK-Tailored Prophylactic Treatment Regimen

Subjects may decide to receive a PK-tailored prophylactic treatment regimen to maintain a FVIII trough level of $\geq 3\%$. The dose should not exceed 80 IU/kg and the FVIII peak levels should not exceed 200%.

Subjects choosing a PK-tailored prophylactic treatment who did not undergo a PK assessment in a previous BAX 855 study will undergo an abbreviated PK assessment with 1 pre- and 6 post-infusion sampling times up to 96 ± 4 hours (for subjects aged ≥ 12 years) or 1 pre- and 3 post-infusion sampling times up to 56 ± 4 hours (for subjects aged < 12 years) following the infusion of 60 ± 5 IU/kg of BAX 855.

Based on the subject's individual PK, the dose will be calculated to ensure FVIII target trough levels in plasma of $\geq 3\%$. The dose will be calculated by the sponsor and provided to the study site. The frequency of dosing will be at least twice weekly or more, depending on subject's $T_{1/2}$ and preference for treatment schedule.

Subjects must adhere as closely as possible to the dosing regimen. If a dose is missed, it must be documented and the next dose will be taken as soon as possible. After this dose, the regularly scheduled regimen will be resumed. Subjects requiring treatment for a breakthrough bleeding episode should resume their PK-tailored prophylaxis as soon as the bleeding episode is resolved.

In order to ensure the required washout periods of at least 84 to preferably 96 hours prior to study visits^v, the scheduled regimen may be interrupted for this period but should be resumed once the study visit is completed. For the determination of FVIII trough levels at visit 4 ± 1 , 8 ± 1 and 18 ± 2 weeks following baseline, no wash-out period is required. The visits should be planned so that a blood sample can be drawn immediately prior to a regularly planned prophylactic infusion.

v For subjects on a more than twice weekly dosing regimen, every attempt should be made to adhere to the minimum washout period of 84 hours.

8.7.3.4 BAX 855 Dose and/or Frequency Adjustments for Subjects on PK-Tailored Prophylactic Treatment Regimen

Subjects meeting any of the following criteria during their PK-tailored prophylaxis may have their BAX 855 dosage and/or infusion frequency increased:

- Two or more spontaneous (not trauma-related) bleeding episodes in the same target joint within any 2-month period

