13.4.6 Exploratory Outcome Measures

Patient satisfaction with treatment, patient activity level and health resource use data will be descriptively summarized and listed.

The potential influence of TGA parameters and FVIII trough levels on ABR in the three months after TGA/FVIII trough level measurement will be explored by scatterplots for all subjects who have TGA tested.

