20.2.2.5 Follow-up Visits: Every 3 Months (\pm 2 Weeks) Starting from Baseline Visit

A washout period of at least 84 h to preferably 96 hours must have elapsed since the previous BAX 855 administration and the subject must not be actively bleeding.

The following assessments will be performed:

Pre-infusion:

- Physical examination, including height (for subjects aged < 18 years at enrollment) and body weight
- Review and discuss subject e-diary, including:
 - Review bleeding episodes and their treatment
 - Adverse events
 - Concomitant medications and non-drug therapies
- Laboratory assessments within 30 minutes of start of infusion:
 - FVIII activity and antigen
 - TGA parameters and VWF antigen (optional in subjects aged < 12 years)
 - Immunogenicity tests
 - Hematology, clinical chemistry and lipid panel
- Vital signs (within 15 minutes of IP infusion)

Determination of IR:

- Infusion of 60 ± 5 IU/kg BAX 855

Post-infusion

At 30 ± 15 min post-infusion:

- FVIII activity and antigen
- TGA parameters (optional in subjects aged < 12 years)
- Vital signs

Other procedures:

- Dispense IP:
 - A sufficient quantity of IP will be dispensed to cover the period until the next scheduled visit (ie, for 5 or 8 weeks or 3.5 months, depending on the visit).
- Dose adjustments as needed.

Intermittent procedures, every 6 months:

- Every 6 months PROs will be assessed:
 - Bleed and pain severity using Haemo-SYM (≥ 18 years), HRQoL using SF-36 (≥ 14 years), HRQoL using PedsQL (< 14 years), patient satisfaction with treatment using the Satisfaction Questionnaire (all ages), and Patient Activity Level (all ages).
- In subjects who are HIV positive, CD4 counts should be tested every 6 months.

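### The three-month ABR after a trough or TGA measurement is counted over a window that the visit schedule does not provide, and it has no matching denominator

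*SAP*

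**What the plan says.** Protocol 13.4.6 plans to explore how TGA parameters and FVIII trough levels bear "on ABR in the three months after TGA/FVIII trough level measurement". SAP 10.5 takes this over and wants each subject's values "plotted in a scatter plot against the ABR of the three months after FVIII trough level and TGA measurement". A fitted line is added to the graph. To obtain that ABR it refers to SAP 7.1 and adds an instruction: "counting the bleeds to the next scheduled visit (which is scheduled every three months").

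SAP 7.1 defines the ABR as the number of distinct bleeds divided by the observation period for efficacy (OPE), in years, on the treatment regimen. It gives no denominator for a window that starts at a measurement.

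The protocol sets these visits:

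- PK-tailored subjects have FVIII, TGA and VWF antigen measured "at 4, 8 and 18 weeks after the baseline visit" (Protocol 8.2). Section 8.7.3.3 gives the windows: "trough levels at visit 4 ± 1 , 8 ± 1 and 18 ± 2 weeks following baseline".
- These visits lie between the quarterly ones, which Protocol 8.2 describes as "subsequent visits every 3 months following their baseline visit".
- Protocol 20.2.2.5, on product supply from a quarterly visit to the next visit, gives the interval as "ie, for 5 or 8 weeks or 3.5 months, depending on the visit".
- Fixed-dose subjects return at 6 weeks and then every 3 months from screening or baseline.

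**The concern.** The SAP asks for a three-month quantity and then defines it by a visit interval that it takes to be three months. If the next visit comes sooner, the count stops sooner, and what is plotted is not what the protocol asked for. Because the denominator is also left open, two programmers could follow the same paragraph and produce different plots.

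The second exploratory objective (Protocol 7.4) is to relate TGA, trough level and ABR, and these plots are its only planned analysis. If a shortened count is divided by a longer period, the understatement differs by visit, so points on different scales share one regression line. Trough results can lead to dose adjustment, so trough level may itself change with visit number. The visit-dependent error could then distort the slope as well as the level.

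**Working it through.** **Inputs.** PK-tailored visits after baseline are at weeks 4 ± 1, 8 ± 1 and 18 ± 2 and every 3 months ± 2 weeks (Protocol 8.7.3.3 and 20.2.2.5). The SAP's year is 365.2425 days (SAP 6.7), so three months = 365.2425/4 = 91.3 days = 13.04 weeks.

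**Step 1: test the stated interval.** Gap = next visit minus current visit. Factor = 13.04/gap, which is the understatement if a count that stops at the next visit is divided by three months.

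| From → next visit | Nominal gap (weeks) | Gap at window extremes | Factor |
|---|---|---|---|
| PK-tailored baseline → week 4 | 4.00 | 3.0–5.0 | 3.26 |
| Week 4 → week 8 | 4.00 | 2.0–6.0 | 3.26 |
| Week 8 → month 3 | 5.04 | 2.0–8.0 | 2.59 |
| Month 3 → week 18 | 4.96 | 1.0–9.0 | 2.63 |
| Week 18 → month 6 | 8.09 | 4.1–12.1 | 1.61 |
| Month 6 → month 9 | 13.04 | 9.0–17.0 | 1.00 |
| Fixed-dose start → week 6 | 6.00 | not computed | 2.17 |
| Fixed-dose week 6 → month 3 | 7.04 | not computed | 1.85 |

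On the PK-tailored schedule the three-month interval appears only from month 6. After weeks 4, 8 and 18 the gap stays below 13.04 weeks even at the widest visit windows.

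**Step 2: the alternative reading.** If the next scheduled visit means the next quarterly visit, the gaps after weeks 4, 8 and 18 are 9.04, 5.04 and 8.09 weeks (factors 1.44, 2.59 and 1.61). None is three months.

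**Step 3: the denominator.** Take a true rate of 4 bleeds per year. The expected count in a 4-week window is 4 × 28/365.2425 = 0.307. For 5.04 and 8.09 weeks it is 0.387 and 0.620.

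- *Three months (0.25 year):* 0.307/0.25 = 1.23, 0.387/0.25 = 1.55 and 0.620/0.25 = 2.48, instead of 4. These are the factors 3.26, 2.59 and 1.61.
- *Regimen OPE, as SAP 7.1 literally reads:* the OPE is not known in advance. I assume 0.25 to 1 year, in line with the planned 3 to 12 months of participation in Protocol 8.3. The 4-week count then gives 0.307/0.25 = 1.23 down to 0.307/1 = 0.31, which is 3.3- to 13-fold too low. A longer OPE would make it lower still.
- *Actual time to the next visit:* 0.307/(28/365.2425) = 4.0, so there is no bias. The rate is noisier, however: one bleed in 4 weeks gives 365.2425/28 = 13.0 per year, against 4.0 for one bleed in three months.

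**Step 4: look for a rule elsewhere that repairs this.** SAP 5.6 presents data by nominal visit and does not reassign visits. SAP 5.7 lists changes from the protocol analysis and does not mention this one.

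**The case against.** The strongest reply is that counting to the next visit is a reasonable design. It gives windows that do not overlap, and it pairs each level with the bleeding before the next measurement and any resulting dose change. If the count is divided by the actual time, the rate is unbiased. The output is an exploratory scatterplot with no hypothesis test or sample size behind it. From month 6 on the PK-tailored schedule, and from month 3 on the fixed-dose schedule, the visits are three months apart, as the SAP says.

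Much of this stands. It limits the consequence and shows that a next-visit window could be defended. But the SAP does not choose that window on those grounds: it presents it as three months long. Nor does it say to divide by actual time, and its cross-reference points to a different denominator.

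A reader might infer two stronger claims that the documents do not support:

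- *The rate is simply wrong by up to about threefold.* That needs a three-month denominator, which the SAP does not state. At week 4 it also needs the next visit of any kind to be the one meant.
- *The error falls on exactly the genuine trough samples.* Protocol 12.7.4.3 also calls the pre-infusion level at incremental recovery visits a trough. Short gaps also follow the PK-tailored baseline and month 3 visits and the early fixed-dose visits.

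**Conclusion.** The point holds as a contradiction between SAP 10.5 and the protocol schedule, together with an unspecified denominator. No reading of the next scheduled visit gives a three-month window after the PK-tailored trough visits at weeks 4, 8 and 18.

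The numerical error cannot be stated as one figure. It ranges from no bias (actual time), through the factors of about 3.3, 2.6 and 1.6 at weeks 4, 8 and 18 (three-month denominator), to as much as 13-fold for a 4-week count (regimen OPE at the upper end of the assumed range). Where there is bias, it is an understatement. These figures use nominal visit dates and a constant bleed rate.

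Only the exploratory trough and TGA plots and their regression line are affected. No primary or secondary result changes.

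**What to change.** In SAP 10.5, replace the next-visit rule with one sentence. For each measurement, count bleeds from the time of measurement to the earlier of 91 days or the end of the observation period, whatever visits fall in between. Divide by that actual time in years, not by the regimen OPE of Section 7.1. At a true rate of 4 per year this returns 4.0 at every visit.

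Do not end the window at a dose or regimen change. Under Protocol 8.7.3.2 and 8.7.3.4, spontaneous joint bleeds and low troughs are themselves criteria for such a change. Stopping there would shorten follow-up selectively in subjects who bleed or have low levels, and could raise their ABR along the axis being plotted.

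The cost is small. Bleed onset dates and times are already in the e-diary (Protocol 10.5.1), so no new data are needed. The one downside is overlap: 13-week windows from weeks 4, 8, 13 and 18 run to about weeks 17, 21, 26 and 31, so a bleed in week 15 would enter three points for the same subject. A footnote should say so, and the regression line should be treated as descriptive.
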